Safety will be represented in the composite device-related adverse event rate which will be reported with its 95% two-sided exact confidence interval. The composite device-related adverse event rate will be assumed to follow the Binomial Distribution. The DSMB will decide the clinical acceptability of this observed event rate in assessing trial success.

Additionally each event will be presented with its respective rate and confidence interval. Death will be separated into deaths that occur before 30-days post-procedure and those that occur between 30-days post-procedure and 6 months.

Efficacy measurements

The efficacy of C-Pulse® will be evaluated by assessing the change of the efficacy variables from baseline to 6 months post-implant. The following measurements will be taken at baseline and 6-months.

- Peak VO₂
- Quality of Life as measured by the Minnesota Living with Heart Failure (MLWHF)
- HF Symptoms as measured by NYHA
- Six Minute Hall Walk Test

Performance Requirement

Trial success will be evaluated by analyzing each patient's response to the four efficacy variables. A responder analysis will be performed for each patient assessing the response to each of the four efficacy variables. Each efficacy variable will be assessed for clinical improvement ("responder"), decline ("non-responder") or no change ("indeterminant").

Clinical improvement will be defined for each efficacy variable as:

- 1.2 ml/kg/min improvement in peak VO₂
- 7 point improvement in MLWHF score
- 1 class improvement in NYHA
- 50 meter improvement in the Six Minute Hall Walk

Clinical decline will be defined for each efficacy variable as:

- 1.2 ml/kg/min decrease in peak VO₂
- 7 point decrease in MLWHF score
- 1 class decrease in NYHA
- 50 meter decrease in the Six Minute Hall Walk

A patient that shows no improvement or decline in a particular endpoint will be labeled as "indeterminate" for that endpoint.

The overall percentage of responders, non-responders and indeterminates for each efficacy variable along with the respective 95% two-sided exact confidence interval will be presented. Additionally the point estimate for the average change and its respective standard deviation will be presented for peak VO₂, MLWHF, and the Six Minute Hall Walk. The improvement in NYHA will be presented by a cross-tabulation summary. The DSMB will decide the clinical acceptability of this responder analysis in assessing trial success.

Secondary Objectives

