APPENDIX N: QUALITY OF LIFE QUESTIONNAIRES

MINNESOTA LIVING WITH HEART FAILURE QUESTIONNAIRE

This questionnaire is to be completed by the patient, after receiving basic instruction from the Clinical Investigator or Research Nurse (Instructor). All attempts should be made to administer the questionnaire:

- by the same person each time, in same setting
- before any other scheduled investigations or medical reviews
- in isolation from spouse and/or other persons who might affect the answers

Furthermore, the Instructor will not paraphrase the pertinent question if asked about the question, but just reiterate the pertinent instructions and the question itself, then ask the patient to respond according to what he or she thinks is appropriate

Begin by showing the patient the questionnaire and asking that they answer a few questions.

Tell the patient to read and think about each question carefully and telling them to make sure to answer all questions. Then go through the first question with him/her to make sure the instructions are clear – indicate that over the last month only.

“If the answer is No then you circle the zero (point to zero). If the answer is Yes, then how much did it stop you living as you wanted over the last month – how much did it prevent you doing things, or how bothersome was it?

Circling 1 means little effect, and circling 5 means very much effect. The 2–4 represent a range of effect in between little and very much.

Did your heart failure prevent you from living as you wanted during the last month by:	No	Very Little	Very Much			
	0	1	2	3	4	5
1. causing swelling of your ankles, legs, etc.?	0	1	2	3	4	5
2. making you sit or lie down to rest during the day?	0	1	2	3	4	5
3. making your walking about or climbing stairs difficult?	0	1	2	3	4	5
4. making your working around the house or yard difficult?	0	1	2	3	4	5
5. making your going places away from home difficult?	0	1	2	3	4	5
6. making your sleeping well at night difficult?	0	1	2	3	4	5
7. making your relating to or doing things with your friends and family difficult?	0	1	2	3	4	5
8. making your working to earn a living difficult?	0	1	2	3	4	5
9. making your recreational pastimes, sports, or hobbies difficult?	0	1	2	3	4	5
10. making your sexual activities difficult?	0	1	2	3	4	5
11. making you eat less of the food you like?	0	1	2	3	4	5
12. making you short of breath?	0	1	2	3	4	5
13. making you tired, fatigued, or low in energy?	0	1	2	3	4	5
14. making you stay in a hospital?	0	1	2	3	4	5

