APPENDIX O: HEART FAILURE ASSESSMENTS

NYHA Classification

In 1928, the New York Heart Association published a classification of patients with cardiac disease based on clinical severity and prognosis. This classification has been updated in seven subsequent editions of Nomenclature and Criteria for Diagnosis of Diseases of the Heart and Great Vessels (Little, Brown & Co.). The ninth edition, revised by the Criteria Committee of the American Heart Association, New York City Affiliate, was released March 4, 1994. These classifications are summarized below.

Class I. Patients with cardiac disease but without resulting limitation of physical activity. Ordinary physical activity does not cause undue fatigue, palpitation, dyspnea, or angina.

Class II. Patients with cardiac disease resulting in slight limitation of physical activity. They are comfortable at rest. Ordinary physical activity results in fatigue, palpitation, dyspnea, or angina.

Class III. Patients with cardiac disease resulting in marked limitation of physical activity. They are comfortable at rest. Less than ordinary activity causes fatigue, palpitation, dyspnea, or angina.

Class IV. Patients with cardiac disease resulting in inability to carry on any physical activity without discomfort. Symptoms of heart failure or the anginal syndrome may be present even at rest. If any physical activity is undertaken, discomfort is increased.

ACC/AHA Stages of Heart Failure

In 2001, the ACC/AHA published an update subdividing clinical heart failure into four ‘stages’. The stages are listed below.

Stage A. Patients at high risk for developing clinical HF (i.e. those with hypertension, diabetes, dyslipidaemia, and so on), but without detectable structural heart disease.

Stage B. Patients with detectable structural heart disease (i.e. LVH, LV Dysfunction), but no clinical signs or symptoms of HF.

Stage C. Patients with current or past clinical HF.

Stage D. Patients with end-stage refractory HF, who are candidates for extraordinary forms of therapy or for compassionate end-of-life care.

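### Clinical decline is defined in the wrong direction for MLWHF and NYHA, so improvers also meet the non-responder rule and worseners become indeterminate

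*Combined protocol and SAP*

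**What the plan says.** Under Statistical Methods and Data Analysis, the Performance Requirement for the efficacy measurements describes a responder analysis on peak VO₂, MLWHF, NYHA and the six minute hall walk. Improvement makes a patient a responder, decline a non-responder, and anyone with neither is indeterminate.

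- Improvement is given without a numeric direction, for example "7 point improvement in MLWHF score" and "1 class improvement in NYHA".
- Decline is given as a decrease on all four: "1.2 ml/kg/min decrease in peak VO₂", "7 point decrease in MLWHF score", "1 class decrease in NYHA" and "50 meter decrease in the Six Minute Hall Walk".

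The percentage in each category is to be reported for each variable with an exact 95% interval, and the DSMB judges the acceptability of the result when assessing trial success.

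The appendices fix the direction of the two scales in question. In Appendix N each MLWHF item runs from 0 (no effect) upwards: "Circling 1 means little effect, and circling 5 means very much effect". In Appendix O, NYHA Class I is no limitation and the scale ends at "Class IV. Patients with cardiac disease resulting in inability to carry on any physical activity without discomfort". The Clinical Need section also treats a move from Class III/IV to Class I/II as an improvement.

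**The concern.** One word, decrease, is applied to four scales that do not point the same way. For MLWHF and NYHA the decline rule therefore describes a patient who got better. Two things follow: an improver satisfies two categories that should exclude each other, and a patient who deteriorates satisfies neither and drops into the category meant for no change.

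This is the plan's only stated efficacy rule for judging success. The study has no hypothesis test or power calculation, so the DSMB works from these percentages and intervals together with the safety rate. The category that disappears is worsening, in a single-arm, open-label study of a surgically implanted device. The effect may also spread: the Secondary Objectives section evaluates consistent endpoints at the other time points, and the Sample Size Determination section says estimates from this study will be used to power the pivotal trial.

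**Working it through.** The plan gives no figure to reproduce here, so the check applies the written rules to every possible outcome.

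**Inputs.** Thresholds of 7 points and 1 class (Performance Requirement), read as at least that much. MLWHF has 21 items scored 0 to 5 (Appendix N); assuming they are summed, the total runs from 0 to 21 × 5 = 105. NYHA runs from I to IV (Appendix O). Let d = 6-month value minus baseline; on both scales negative d is better.

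**Rules.** Improvement: d ≤ −7 (MLWHF) or d ≤ −1 (NYHA). Decline as written: the same two conditions. Decline as intended: d ≥ 7 or d ≥ 1.

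**All baseline and 6-month pairs.** MLWHF has 106 × 106 = 11,236 pairs. Those with a fall of at least 7 number 99 + 98 + … + 1 = 99 × 100 / 2 = 4,950. By symmetry 4,950 have a rise of at least 7, leaving 11,236 − 9,900 = 1,336. NYHA has 16 pairs: 6 better, 6 worse, 4 unchanged.

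| True change | MLWHF pairs | NYHA pairs | As written | As intended |
|---|---|---|---|---|
| Better | 4,950 | 6 | responder and non-responder | responder |
| Worse | 4,950 | 6 | indeterminate | non-responder |
| Neither | 1,336 | 4 | indeterminate | indeterminate |

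No pair on either scale is a non-responder only. The same check on peak VO₂ (±1.2) and walk distance (±50 m) classifies correctly.

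**Illustration.** The counts are assumed, not taken from the plan: n = 40 with 20 improved, 12 unchanged and 8 worse, and exact 95% intervals.

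| Category | As written | As intended |
|---|---|---|
| Responder | 20/40 = 50% (33.8–66.2) | 20/40 = 50% (33.8–66.2) |
| Non-responder | 20/40 = 50% (33.8–66.2) | 8/40 = 20% (9.1–35.6) |
| Indeterminate | (12 + 8)/40 = 50% (33.8–66.2) | 12/40 = 30% (16.6–46.5) |
| Total | 150% | 100% |

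In general the written total is 100% plus the responder percentage, because each improver is counted twice. Other assumed splits at n = 20 show the range:

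- 5 improved, 7 unchanged, 8 worse: non-responders are 25% as written against 40% as intended; the written total is 125%.
- 15 improved, 4 unchanged, 1 worse: non-responders are 75% as written against 5% as intended; the written total is 175%.

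**If the code tests improvement first and stops there,** the double count vanishes. The n = 40 example becomes 20 responders, 0 non-responders and 20 indeterminate. That totals 100%, and on these two scales the non-responder count would be zero whatever the data.

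**The case against.** The strongest reply is that the intent is plain. The list is headed as clinical decline, the section sets up three opposed outcomes, and decrease is probably a loose opposite of improvement reused down the list. A competent programmer might code it correctly. The NYHA line is also weaker evidence than the MLWHF line: it mentions no score and could mean losing a class of function. The responder percentage does not change. A NYHA cross-tabulation and the MLWHF mean change with its standard deviation are also reported, no numeric success threshold is attached, safety is the primary endpoint, and a table totalling 150% would be noticed.

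Much of this is fair and limits the damage. The responder figures do stand, and the NYHA cross-tabulation should show moves from Class III to IV. But a mean and standard deviation do not say how many patients worsened on MLWHF, and the wording there is explicitly about the score. Nothing elsewhere in the plan restates the decline rule in the right direction. A total above 100% is a safeguard only if overlaps are left in; code that tests improvement first gives a tidy 100% with no non-responders. A silent correction in code, or one made after the data are seen, would also depart from the written rule on an analysis used to judge success.

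**Conclusion.** The concern holds. The decline rule is reversed for MLWHF beyond reasonable dispute, and for NYHA on the ordinary reading of a decrease in class. Followed literally, it double-classifies every improver and labels every worsener indeterminate on two of four efficacy variables. In the 40-patient illustration the non-responder percentage is 50% instead of 20% and the indeterminate percentage 50% instead of 30%.

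The size of the error depends on the assumed patient counts; the failure of the classification does not. The enumeration assumes a summed MLWHF total and thresholds read as at least the stated change. This is most likely a drafting slip, but it sits in an operative rule and must be corrected before the analysis is run.

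**What to change.** Rewrite the two lists with a numeric direction for every variable:

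| Variable | Improvement | Decline |
|---|---|---|
| Peak VO₂ | rises by ≥ 1.2 ml/kg/min | falls by ≥ 1.2 ml/kg/min |
| MLWHF total score | falls by ≥ 7 points | rises by ≥ 7 points |
| NYHA class number | falls by ≥ 1 | rises by ≥ 1 |
| Six minute hall walk | rises by ≥ 50 m | falls by ≥ 50 m |

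Add that the three categories are mutually exclusive and exhaustive among patients with both assessments, and apply the same definitions wherever the endpoints are repeated at other time points. With this change every MLWHF and NYHA pair in the enumeration falls in exactly one category. The cost is a wording amendment to the statistical section; no new data are needed, and the sample size is unaffected.

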Progression to the Pivotal study will be based on the assessment for safety of the device and indicators of performance. Baseline and follow-up data will be used to assess any significant difference in quality of life and functional variables pre and post implant and to assess the effect of counterpulsation.

Following successful completion of this Feasibility Study, a pivotal study will be conducted to examine the safety and efficacy of the C-Pulse® system in patients in moderate to severe heart failure. The pivotal trial is expected to measure the same variables as the Feasibility Study.

The total duration of the Feasibility Study is expected to be approximately 120 months or until the study is closed.

OBJECTIVES

Primary Objectives

Following are the primary objectives for this study. The primary objective of the C-Pulse feasibility study is to assess safety, while at the same time obtain performance data for evidence of efficacy to assist planning for a pivotal study. Refer to the section on Statistical Methods and Data Analysis for a detailed discussion of the definitions and methodology.

The Clinical Investigation shall:

1. Assess the risks with regard to the performance of the device as defined by the serious adverse event rates, under normal conditions of use.
2. Assess the potential benefits of C-Pulse as defined by improvements in Peak VO₂, hemodynamic measures, quality of life and HF symptoms.

Secondary Objectives

Secondary objectives are intended to provide additional information on patient response and device performance and to allow planning for the pivotal study. The secondary objectives are as follows:

1. Further assess the potential risks with regard to the performance of the device as defined by the device failure rate, adverse event rates, adverse event attribution, re-hospitalization rates, duration of support, and length of time to hospital discharge.
2. Further assess the potential benefits of C-Pulse as defined by improvements in quality of life, fatigue impact scales, hemodynamics, average distance walked in the 6 minute hall walk test, and blood tests.
3. Assess the device usage.

Together the primary and secondary objectives will:

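### Efficacy success is judged from responder percentages, but no improved-versus-declined contrast, no-change reference rate, within-patient summary or interval for mean change is pre-stated

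*Combined protocol and SAP*

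**What the plan says.** Under Efficacy measurements, Performance Requirement, the basis for judgement is the patient: "Trial success will be evaluated by analyzing each patient's response to the four efficacy variables". Each variable is classed as improved, declined or neither, using thresholds of equal size in both directions: 1.2 ml/kg/min for peak VO2, 7 points for MLWHF, 1 class for NYHA and 50 m for the six minute walk.

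The outputs are then listed variable by variable:

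- On the three response categories, the text reads "The overall percentage of responders, non-responders and indeterminates for each efficacy variable along with the respective 95% two-sided exact confidence interval will be presented".
- On mean change, which gets no interval or test, it reads "Additionally the point estimate for the average change and its respective standard deviation will be presented for peak" VO2, and likewise for MLWHF and the walk test.
- On functional class, it reads "The improvement in NYHA will be presented by a cross-tabulation summary".

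The decision is left to judgement: "The DSMB will decide the clinical acceptability of this responder analysis in assessing trial success".

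The Design section, repeated in the Study Summary (Appendix R), says that baseline and follow-up data "will be used to assess any significant difference in quality of life and functional variables pre and post implant". The opening of the statistics section says the study is not powered for statistical significance and that clinical judgement is needed. Sample Size Determination adds that the estimates will be used to power the pivotal study.

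**The concern.** Success is framed per patient, yet every planned output is a marginal summary of one variable. From those marginals nobody can tell whether the same patients improve across several measures or different patients improve on each.

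A responder percentage from a single-arm study also has no natural zero. Test-retest variation alone carries some patients past each threshold, so an interval that excludes 0% says little. The useful comparison is with the share who declined by the same amount, or with a stated no-change rate. The plan specifies neither.

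The Design section promises an assessment of significant change, but the statistics section contains no analysis that would deliver it. At stake are how the DSMB reads a moderate responder rate and how precisely the estimates carried into pivotal-trial planning are reported.

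**Working it through.** **Inputs from the documents.** The thresholds are as listed above; for example, "1.2 ml/kg/min improvement in peak" VO2. The number implanted is 20 in Sample Size Determination and 40 in the expanded Design section, so both are shown. The figure of 20 is justified on clinical grounds with no effect size, SD or precision target, so there is no calculation to reproduce.

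**Assumption.** The documents give no SD of change. I take it as 0.75 to 2 times the threshold, with normally distributed change and zero true mean.

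**Step 1: responder rate with no change.** P(responder) = 1 − Φ(threshold / SD). By symmetry the same share are decliners. The last two columns give the binomial chance of seeing 30% or more responders (at least 6 of 20, or 12 of 40) on one variable.

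| SD ÷ threshold | SD: VO2 (ml/kg/min), MLWHF (points), walk (m) | Responders | ≥30%, n = 20 | ≥30%, n = 40 |
|---|---|---|---|---|
| 0.75 | 0.9, 5.25, 37.5 | 9.1% | 0.7% | below 0.1% |
| 1 | 1.2, 7, 50 | 15.9% | 8.4% | 1.8% |
| 1.5 | 1.8, 10.5, 75 | 25.2% | 39.3% | 29.8% |
| 2 | 2.4, 14, 100 | 30.9% | 61.6% | 60.5% |

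The exact 95% interval is 11.9% to 54.3% for 6 of 20 and 16.6% to 46.5% for 12 of 40. Both exclude 0%, but 0% is not the no-change value in any row.

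**Step 2: what the contrast adds.** Take 8 responders of 20 (40%, exact interval 19.1% to 63.9%). For improved share p₁ and declined share p₂ in the same n patients, SE = √[(p₁ + p₂ − (p₁ − p₂)²)/n].

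- 8 improved, 7 declined: difference 5%; SE = √[(0.40 + 0.35 − 0.0025)/20] = 0.193; approximate 95% interval −33% to +43%.
- 8 improved, 1 declined: difference 35%; SE = √[(0.40 + 0.05 − 0.1225)/20] = 0.128; approximate 95% interval +10% to +60%.

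The responder percentage and its interval are the same in both cases; the contrast separates them.

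**Step 3: the missing interval for mean change.** Half-width = t(0.975, n−1) × SD/√n, which is 0.47 SD at n = 20 and 0.32 SD at n = 40. With SD at 1 to 2 times the threshold:

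- n = 20: ±0.56 to ±1.12 ml/kg/min, ±3.3 to ±6.6 MLWHF points, ±23 to ±47 m.
- n = 40: ±0.38 to ±0.77 ml/kg/min, ±2.2 to ±4.5 points, ±16 to ±32 m.

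**The case against.** The strongest reply is that this is an openly descriptive feasibility study and that the needed information is largely there. Much of that stands.

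- The plan reports declined and unchanged percentages as well as improved ones, all with exact intervals. Because the decline thresholds mirror the improvement thresholds, an attentive reader already has an implicit check on symmetric noise.
- The interval for mean change follows from the mean, SD and n, and the improved-minus-declined difference follows from the reported percentages. The DSMB includes a biostatistician who could work out both. These are gaps in pre-stated reporting, not lost data. Only the within-patient pattern cannot be recovered from the planned tables.
- Assessing variables separately was deliberate. The revision history (Appendix V) records removal of a heart failure composite in favour of individual assessment, and later shaping of the responder analysis on FDA feedback. That argues against a net score used as an endpoint, but not against a descriptive table.
- Familiarization tests, a blinded core lab for exercise testing and standardized MLWHF administration all reduce noise. They may place the SD in the lower part of the assumed range, but they do not supply a reference rate.

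A reader might infer that noise and effect cannot be told apart under this plan. For random noise the documents do not support that, for the first two reasons above. Nor do they support quoting the chance of improving on any one of several variables as a false-success rate, since no such success rule is written. Classifying the changes does not discard the continuous information either, because mean and SD are also reported.

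**Conclusion.** The point holds as a modest, inexpensive gap. The plan judges success per patient and speaks of significant pre-post differences, but gives the DSMB no pre-stated yardstick for separating random variation from change. On the assumed range of SDs, about 9% to 31% responders on a variable would be unremarkable with no true mean change, provided a similar share declined. Those figures illustrate the issue and are not estimates for this population; they rest on an assumed SD and on normality.

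The added outputs address random variation only. A reader might take a positive difference as evidence of device effect. In a single-arm, open-label study with entry limits on peak VO2 and walk distance, it could equally reflect regression to the mean, open-label response or time trend.

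**What to change.** In the efficacy Performance Requirement, add:

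- **Mean change:** a 95% t interval for peak VO2, MLWHF and six minute walk, labelled descriptive.
- **Contrast:** for each variable, percent improved minus percent worsened, with a 95% interval that allows for both counts coming from the same patients. Note that zero may not be the no-change value for NYHA, because a patient entering in Class IV cannot worsen by a class. Define improvement by direction of benefit: the decline list counts a 7 point decrease in MLWHF as worsening, although higher answers on the Appendix N form mean greater limitation.
- **Within patient:** a descriptive table of how many of the four variables each patient improved on and worsened on, stated not to be a composite endpoint.

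In the Design section and Appendix R, replace the promise to assess significant differences with one to estimate the change, in line with the opening of the statistics section. Beside the tables, state that without a control group they cannot separate device effect from regression to the mean, open-label response or time trend.

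The cost is some wording and a few table columns from data already collected. The efficacy message may look less favourable.
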